## 8.2 Secondary Analyses of Vaccine Efficacy

### 8.2.1 Modified Intention to Treat Vaccine Efficacy Estimate

As a key secondary analysis, we report the MITT vaccine efficacy from Months 0-24, i.e.  $VE(0-24)$ . This analysis is conducted within the MITT cohort of participants who are HIV-1 uninfected on the date of first vaccination. **The failure times of MITT participants for the analysis of  $VE(0-24)$  are right-censored following the same approach as used for the primary analysis of vaccine efficacy.** We define the MITT vaccine efficacy as one minus the probability of the MITT efficacy endpoint between the month 0 and month 24 visit for the vaccine group divided by the probability of the MITT efficacy endpoint between the month 0 and month 24 visit for the placebo group times 100 percent. The VE parameter  $VE(0-24)$  will be estimated at the same time point  $\tau$  as defined in Section 8.1. Each of the two cumulative incidence parameters in  $VE_{0-24}(\tau)$  will be estimated using the transformed Nelson-Aalen estimator for the cumulative hazard function evaluated at time  $\tau$  defined in Section 8.1.

This key secondary analysis tests

$$\begin{aligned} & \text{the null hypothesis } H_0: VE_{0-24}(\tau) = 0 \text{ versus} \\ & \text{the alternative hypothesis } H_1: VE_{0-24}(\tau) \neq 0 \end{aligned} \tag{2}$$

using a 2-sided  $\alpha = 0.05$  level Wald test of the equality of log cumulative hazard functions at  $\tau$  for the vaccine group and the control group within the MITT cohort.

Cox proportional hazards model will also be used for estimating  $VE(0-24)$ , measured by 1 minus the hazard ratio (vaccine vs. placebo) and for a score test of whether the  $VE(0-24)$  differs from 0%.

### 8.2.2 Vaccine Efficacy Estimates that Adjusts for Covariates

As a supportive analysis of the hypotheses in (1), a doubly robust estimator will be used to estimate cumulative incidences of the primary efficacy endpoint over time in the per protocol population, accounting for both per-protocol and right censoring status. The estimator used for this analysis is described in Westling et al. (2021). Super Learner (van der Laan, Polley, and Hubbard, 2007; Westling, Luedtke, Gilbert, and Carone, 2021) is used to generate initial estimates of the conditional protocol violation and censoring distribution and the iterated conditional means. The Super Learner library is specified in Table 2. If any of the algorithms included in the Super Learner library return an error when run on the trial data (e.g., due to the rarity of the event), then they will be removed. Each method considers adjustment for vaccine/placebo assignment, baseline demographic covariates, and the baseline behavioral risk score built via supervised learning as described in Section 8.5. The particular demographic covariates considered are: site, country, and age at enrollment.

VE parameters will be estimated by 1 minus the ratio (vaccine group/placebo group) of the estimates of the HIV incidence probability between months 7 and 24. Influence-curve based variance estimators of each cumulative incidence are used, and the delta method is applied to obtain the variance estimator of the log cumulative incidence ratio. Point estimates and 95% pointwise and simultaneous Wald CIs for cumulative incidence curves and  $VE(t)$  curves will be plotted. For the final time point of 24 months, 2-sided Wald p-values will be reported.

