### 8.1 Primary Analysis of Vaccine Efficacy

The time between enrollment and the date of HIV-1 infection diagnosis determined in Section 5 is evaluated for all subjects. Subjects becoming HIV-infected or dropping out before their month 7 visit or not having received all of the first 3 vaccinations within the specified time window or having a major protocol deviation will be excluded from the primary PP analysis. **The failure times of participants with last HIV-negative test at or after the month 24 visit are right-censored at the right edge of the month 24 allowable visit window [defined as 60 days after the target day (728 days) for the month 24 visit, equal to 25.91 months post-enrollment]. For participants with last HIV-negative test prior to the month 24 visit and without diagnosis of the HIV-1 infection primary endpoint at or before the month 24 visit, their failure times are right-censored at the date of the last HIV-negative test.**

We define the primary vaccine efficacy parameter,  $VE(7-24)$ , as one minus the probability of the primary efficacy endpoint between the month 7 and month 24 visit for the vaccine group divided by the probability of the primary efficacy endpoint between the month 7 and month 24 visit for the placebo group times 100 percent. **More specifically, the primary VE parameter,  $VE_{7-24}(\tau)$ , will be estimated at the fixed time point  $\tau = 25.91$  months post-enrollment with the specification of the value of  $\tau$  determined as noted above.** Each of the two cumulative incidence parameters in  $VE_{7-24}(\tau)$  will be estimated using the transformed Nelson-Aalen estimator for the cumulative hazard function evaluated at time  $\tau$  defined above. We will use the delta method to obtain the asymptotic 95% CI for the log cumulative incidence ratio (vaccine/control) and then back-transform these confidence bounds to the VE scale. Both the point estimate and the 95% CI for VE will be reported.

$VE(\tau)$  is the target parameter for the primary analysis of overall VE. The primary analysis tests

$$\begin{aligned} &\text{the null hypothesis } H_0: VE_{7-24}(\tau) = 0\% \text{ versus} \\ &\text{the alternative hypothesis } H_1: VE_{7-24}(\tau) \neq 0\% \end{aligned} \tag{1}$$

using a 2-sided  $\alpha = 0.05$  level Wald test of the equality of log cumulative hazard functions at  $\tau$  for the vaccine group and the control group.

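### SAP 8.2.2 still takes its covariate-adjusted p-value at 24 months, while the hypotheses it supports are set at tau = 25.91 months; a cross-reference is missing (minor)

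*SAP*

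**What the plan says.** SAP 8.2.2 opens: "As a supportive analysis of the hypotheses in (1), a doubly robust estimator will be used". It estimates VE as one minus the vaccine/placebo ratio "of the estimates of the HIV incidence probability between months 7 and 24" and sets the time of the test thus: "For the final time point of 24 months, 2-sided Wald p-values will be reported". Tau does not appear in the section.

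Hypotheses (1) are in SAP 8.1. There the right edge of the Month 24 window is "defined as 60 days after the target day (728 days) for the month 24 visit, equal to 25.91 months post-enrollment". The primary VE parameter "will be estimated at the fixed time point" tau, equal to that value, and the primary test is a two-sided 0.05 "level Wald test of the equality of log cumulative hazard functions at" tau.

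Three neighbouring places matter:

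- SAP 8.2.1 (MITT) says explicitly that its parameter is estimated at the tau of 8.1.
- SAP 8.2.3 applies the primary analysis's right-censoring to every analysis of VE through Month 24. It says nothing about the time at which those analyses are evaluated.
- The SAP modification history for version 3.3, which introduced tau = 25.91, lists changes to 8.1, 8.2.1, 8.2.3 and 9. Section 8.2.2 is not listed. Its last logged change is in version 3.2 and concerns the estimation method.

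**The concern.** A supportive adjusted analysis is most useful when it differs from the primary in one respect only, the adjustment. If it is also evaluated at another time, a gap between the adjusted and primary VE mixes the effect of adjustment with a shorter period and fewer endpoints.

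The choice of 24.0 months is not harmless, because the Month 24 target is day 728 and 24.0 months is day 730. Ordinary lateness in scheduling is enough to move a Month 24 diagnosis past the cut. Version 3.2 moved 8.2.2 to a method that does not discretise time, so the analyst has to supply a numeric time point, and the only one in the section is 24. Version 3.3 was written after the final analysis had been run, so an unclear time point also leaves a choice open once results are known.

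**Working it through.** **1. Reproduce tau.** With a month of 365/12 = 30.417 days, (728 + 60)/30.417 = 788/30.417 = 25.907, which rounds to the SAP's 25.91. A month of 365.25/12 days gives 25.89, so the SAP uses 365/12.

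**2. Put both time points on the same scale.**

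| Time point | Months | Day |
|---|---|---|
| Month 24 target (8.1) | 728/30.417 = 23.93 | 728 |
| Test in 8.2.2, read literally | 24.00 | 24 × 30.417 = 730 |
| Tau in 8.1 | 25.91 | 788 |

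The gap is 25.91 − 24.00 = 1.91 months, or 58 days.

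**3. How many Month 24 visits are late?** The version 3.3 entry reports 969 vaccine and 1008 placebo per-protocol women at risk at Month 24. Under the superseded rule, which censored at the Month 24 visit date, 166 and 159 of them remained in the risk set at 24.13 months (24.13 × 30.417 = day 734). So 166/969 = 17.1% and 159/1008 = 15.8%, pooled 325/1977 = 16.4%, had their Month 24 visit on or after day 734. The share after day 730 is not given. I take 16% as the low end and assume 50% as the high end.

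**4. What share of primary endpoints is found at the Month 24 visit?** Design rates (Protocol 6.4.1): placebo incidence 4.2% and dropout 10% per year, total hazard 0.142. With three-monthly testing, infections acquired in Months 21 to 24 are found at Month 24:

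share = [exp(−0.142 × 21/12) − exp(−0.142 × 24/12)] / [exp(−0.142 × 7/12) − exp(−0.142 × 24/12)] = (0.7800 − 0.7528)/(0.9205 − 0.7528) = 0.162.

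The crude ratio 3/17 is 0.176. At half the infection rate (the vaccine arm at VE 50%) the share is 0.164.

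**5. Endpoints left out by a literal 24.0-month cut.** Base: 97, the median number of post-Month 7 infections at VE 50% in Protocol Table 6-5.

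- Low: 0.164 × 0.162 = 2.7%; 97 × 0.0267 = 2.6 endpoints.
- High: 0.50 × 0.162 = 8.1%; 97 × 0.0811 = 7.9 endpoints.

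Simulations with normally scattered visit dates (SD 6 to 10 days), tuned so that 16% of visits fell after 24.13 months, put 27% to 37% of visits after day 730 and lost 4.8% to 6.1% of endpoints, inside this range.

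**6. Effect on power.** By the Schoenfeld approximation with hazard ratio 0.5, power = Φ(√D × ln 2 / 2 − 1.96).

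- D = 97: 92.7% (Protocol Table 6-4, by simulation, gives 90.86%)
- D = 97 − 2.6 = 94.4: 92.0%
- D = 97 − 7.9 = 89.1: 90.5%

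The approximation is used here only for the change, which is 0.7 to 2.2 percentage points.

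**The case against.** The strongest reply is that 24 months is this SAP's label for the corrected analysis. Section 9, in text added in version 3.3, speaks of the analyses through 24 months when it means those evaluated at 25.91. The parameter keeps the name VE(7-24), and 8.2.2 ties itself to hypotheses (1), which are indexed at tau. Reading 8.2.2 as tau is therefore natural, and this stands as a possible reading. It does not settle the matter. The version 3.3 entry uses the phrase final time point for a numeric tau (24.13 months). For the 30-month analyses, Section 9 names the evaluation time and the censoring process as separate items, while 8.2.2 gives no link to either.

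The size is also open to challenge, and this stands. The late-visit fraction comes from women who were still uninfected. Protocol 9.10 and 10.1 allow interim and symptom-prompted testing, so not every infection waits for the Month 24 visit. Visit dates are not in the documents. The 2.6 is the low end of an assumption-based range, not a guaranteed minimum.

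The consequences are limited too. The Section 9 list for the end-of-Stage-1 report does not include the 8.2.2 analysis, and 8.2.2 also asks for cumulative incidence and VE curves over time, so the reader would not depend on one p-value.

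**Conclusion.** The inconsistency is real but minor. As written, 8.2.2 tests at day 730 a set of hypotheses defined at day 788. Under the literal reading it leaves out roughly 3% to 8% of primary endpoints, given the three assumptions on visit timing, scheduled detection and the share of late visits. Power moves by about two points at most.

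Three stronger conclusions might be inferred, and the documents do not support them:

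- *That the version 3.3 correction missed this analysis altogether, so that the loss of over 80% of the risk set recurs.* The general sentence in 8.2.3, as worded, carries the new censoring rule to 8.2.2. Only the evaluation time is left behind.
- *That the TMLE sensitivity analysis in 8.1 has the same fault.* That paragraph targets the primary VE parameter, which the same section fixes at tau. Its mention of Month 24 gives no second numeric time point.
- *That the adjusted VE would be biased.* Nothing in the documents suggests that visit lateness differs by arm. What is shown is a different time point and somewhat fewer endpoints.

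**What to change.** In SAP 8.2.2, replace the 24-month time point in the p-value sentence by the time point tau defined in Section 8.1, with the Section 8.1 right-censoring rule, and make clear that this governs both the adjusted VE estimate and its p-value.

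Use a cross-reference and not the number 25.91. Section 9 puts the window limit for the last participant's Month 24 visit at June 22, 2021, 28 days after the May 25 target, which is (728 + 28)/30.417 = 24.85 months, against 60 days in 8.1. Those two limits need reconciling separately, and a cross-reference will follow whatever is decided.

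The TMLE paragraph in 8.1 needs at most the same cross-reference, for clarity.

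The cost is one phrase in the SAP and one parameter in the code, plus a rerun if the analysis was run at 24.0 months.

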### 8.2.3 Vaccine Efficacy over Time Periods Other Than Months 0–24, Months 7–24

We will repeat the methods from Section 8.1 in the per-protocol cohort in windows other than Months 7-24. In particular, we perform these analyses in the FIS cohort, studying endpoints occurring between Month 13 and 24; and in the FIS cohort, studying endpoints occurring between Month 13 and 36. We will repeat the methods from Section 8.2.1 in the MITT cohort in windows other than Months 0–24. In particular, we perform these analyses among: MITT subjects who are HIV-1 uninfected at Month 13, studying endpoints occurring between Month 13 and 24; MITT subjects who are HIV-1 uninfected at Month 13, studying endpoints occurring between Month 13 and 36; and MITT subjects, studying endpoints occurring between Months 0 and 36.

For all analyses evaluating VE through Month 24, the failure times will be right-censored following the same approach as used for the primary analysis of vaccine efficacy. For analyses that aim to evaluate VE through Month 36, the right-censoring approach used will depend

Table 2: Models included in the Super Learner library.  $Z$  denotes vaccine/placebo assignment,  $B$  baseline behavioral risk score as described in Section 8.5, and  $W$  a vector of baseline demographic covariates. The columns indicate what type of candidate estimator was used (GLM = generalized linear model, step = stepwise GLM using both AIC and BIC as selection criteria, GAM = generalized additive model [additive Cox regression in the case of survival endpoint], RF = random survival forests, KM = Kaplan Meier) and what covariates were included ( $x * y$  indicates a cross product between covariates  $x$  and  $y$ ).

Model type	Covariates
Propensity score estimate	
GLM	$Z$
GLM	$Z + B + W$
GLM	$Z * B$
step	$Z * B + W$
Event and censoring estimates	
KM	$\emptyset$
Cox	$Z$
Cox	$Z * B$
Cox	$Z * B + W$
GAM	$Z + B$
GAM	$Z + B + W$
RF	$Z + B + W$

on the number of participants who attend their month 36 visit at the end of follow-up. The failure time convention right-censoring approach used and definition of the estimand of interest will depend on how large this number is in each of the two arms. In particular:

- Case 1: If at least 150 participants in each arm of the per-protocol cohort have attended their Month 36 visit and had a negative HIV-1 test at that visit, then VE will be evaluated through time  $\tau = 36.5$  months, where 36.5 denotes the upper allowable visit window for the month 36 visit. The failure times of participants with last HIV-1 negative test at or after the month 36 visit are right-censored at the right edge of the month 36 allowable visit window (month 36.5). For participants whose last HIV-1 negative test occurs prior to the month 36 visit and without diagnosis of a primary HIV-1 infection endpoint at or before the month 36 visit, their failure times are right-censored at the date of their last HIV-1 negative test.
- Case 2: If, in at least one of the two arms of the per-protocol cohort, there are not 150 participants that have attended their Month 36 visit and had a negative HIV-1 test at that visit, then, in order to ensure stable estimation, VE will be evaluated through a time  $\tau$  that falls before 36.5 months. The time  $\tau$  will be defined as the maximum

time point at or after which 150 participants in both the vaccine and placebo groups of the per-protocol cohort have HIV-1 negative tests. For participants whose last HIV-1 negative test occurs prior to time  $\tau$  and without diagnosis of a primary HIV-1 infection endpoint at or before time  $\tau$ , their failure times are right-censored at the date of their last HIV-1 negative test. The failure times of all other participants will be right censored at time  $\tau$ .

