The issue is that this specification inadvertently discarded more than 80% of the study participants in the risk-set at the month 24 visit, even though these participants were in fact still at risk at the month 24 visit (defined as HIV negative at all visits with HIV testing results including an HIV negative test result at the month 24 visit). More specifically, for the final analysis data set, 969 per-protocol vaccine recipients and 1008 per-protocol placebo recipients were at-risk at 24 months, yet only 166 per-protocol vaccine recipients and 159 per-protocol placebo recipients were included in the risk-set for the estimation of the cumulative incidence probabilities through the final time point of  $\tau = 24.13$  months. An appropriate survival analysis method should include all of the information in the data, which would include the data from the 969 and 1008 per-protocol participants noted above. The

combination of defining the final time point  $\tau$  to be after the month 24 visit date for most participants ( $\tau = 24.13$  months), and the right-censoring of follow-up times of participants testing HIV negative at month 24 to their month 24 visit dates, caused this problem. The origin of the error was that in group sequential monitoring interim analyses, conducted when only partial follow-up data were available, it was appropriate and useful to define the final time point  $\tau$  of the cumulative incidence and vaccine efficacy parameters based on the latest time point with at least 150 participants at-risk at the latest time point; this ensured stable inference as noted in the v3.2 SAP. However, this issue no longer exists for the final analysis, because for the final analysis all enrolled participants have follow-up well beyond the month 24 visit, such that the condition serves no purpose, and needlessly and inadvertently removes statistical information. Therefore, the carrying over of the statistical method designed for the interim analyses to the final analysis caused the problem.

To remedy this problem, Section 8.1 was revised as follows:

- The v3.2 sentence “The failure times of participants without HIV-1 infection by the month 24 visit are right-censored at the date of the last HIV-negative test or at the month 24 visit, whichever occurs earlier.”

was changed to

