Cox proportional hazards model will also be used for estimating  $VE(7-24)$ , measured by 1 minus the hazard ratio (vaccine vs. placebo) and for a score test of whether the  $VE(7-24)$  differs from 0%.

As a sensitivity analysis to the primary analysis of vaccine efficacy in the PP population, targeted minimum loss-based estimation (TMLE) is used to estimate this vaccine efficacy parameter. TMLE is used to estimate the cumulative incidences of HIV-1 infection over time for each of the vaccine and placebo groups, through to Month 24. These estimates will then be contrasted to estimate the primary VE parameter  $VE(7-24)$ , which adjusts for covariates. This analysis can correct for bias due to measured participant covariates that predict both per-protocol status and HIV-1 infection. As part of the implementation of the TMLE the Super Learner is used to generate initial estimates of the conditional censoring distribution and the iterated conditional means.

In addition, to assess potential time-effects of vaccine efficacy, the Kaplan-Meier method will be used to plot the estimated cumulative incidence rates over time for the vaccine and placebo groups. This method will be used to estimate (i) cumulative vaccine efficacy over time, defined as  $(1 \text{ minus the ratio (vaccine/placebo) of cumulative incidence by time } t) \times 100\%$ , and (ii) additive-difference vaccine efficacy over time, defined as the difference (placebo minus vaccine) in cumulative incidence by time  $t$ , with the method of [Parzen, Wei, and Ying \(1997\)](#) applied to obtain pointwise and simultaneous 95% CIs. In addition, the longitudinal targeted minimum loss-based estimation method as implemented in the R package `survtmle` will be used for estimation, which in addition to allowing confounding adjustment can correct for potential bias due to covariate-dependent censoring.

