    - (b) Repeat 1(a) except for the month 7–30 and 7–36 periods and the PP cohort
    - (c) Repeat 1(b)–(c) except for the month 7–36 period and the PP cohort
    - (d) Repeat 1(a) except for the month 0–30 and 0–36 periods and the MITT cohort
    - (e) Repeat 1(b)–(c) except for the month 0–36 period and the MITT cohort
    - (f) Repeat 1(a) except for the month 13–30 and 13–36 periods and the FIS cohort
    - (g) Repeat 1(b)–(c) except for the month 13–36 period and the FIS cohort
  5. Primary objective 2
    - (a) Maximum local reactogenicity by treatment assignment and the length of reactogenicity follow-up (3 days versus 7 days) (table and figure)
    - (b) Maximum systemic reactogenicity by treatment assignment and the length of reactogenicity follow-up (3 days versus 7 days) (table and figure)
    - (c) Adverse events by system organ class, severity, and treatment assignment (table)
    - (d) Adverse events by preferred term, severity, and treatment assignment (table)

- 
- (e) Adverse events related to study product by preferred term, severity, and treatment assignment (table)
  - (f) Listing of adverse events of special interest (AESIs), by preferred term and severity (listing)
  - (g) Serious adverse events (SAEs) reported to the global safety database ordered by treatment assignment, participant, and decreasing severity (listing)
  - (h) Adverse events leading to early participant withdrawal or early discontinuation of study administrations (listing)
6. Limited demographics and baseline disease characteristics, disposition and adherence tables, by treatment arm

Janssen will propose to the OG a list of recipients at Janssen of the analysis report. The OG's approval will be required before report distribution.

The analyses of vaccine efficacy through 30 months will define the final time point for analysis ( $\tau$ ) and the right-censoring process in the same way as described for the analyses of vaccine efficacy through 24 months, except now indexed off of the month 30 visit instead of the month 24 visit.

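### Month 36 analyses: window-edge censoring covers only the terminal visit, so arm-level cumulative incidence is biased upward when follow-up to Month 36 is incomplete

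*SAP*

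**What the plan says.** Under SAP 5.3 an infection is dated at the draw of the first sample that leads to a positive result. SAP 8.2.3 then sets two censoring rules for analyses through Month 36.

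- **Case 1** applies when each per-protocol arm has at least 150 women with a negative Month 36 test. Tau is then 36.5 months, taken as the latest time the Month 36 window allows. The edge rule reads: "The failure times of participants with last HIV-1 negative test at or after the month 36 visit are right-censored at the right edge", meaning the edge of that window. For uninfected women last tested before that visit, "their failure times are right-censored at the date of their last HIV-1 negative test".
- **Case 2** applies otherwise. Tau is the latest "time point at or after which 150 participants in both the vaccine and placebo groups of the per-protocol cohort have HIV-1 negative tests". Uninfected women last tested before tau are censored on the test date, and the rest at tau.

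The v3.3 entry in the SAP Modification History explains the Month 24 revision. It blames a tau later than most women's visit dates, together with "the right-censoring of follow-up times of participants testing HIV negative at month 24 to their month 24 visit dates, caused this problem". Section 8.1 now carries Month 24 negatives to the window edge, defined as "60 days after the target day (728 days) for the month 24 visit, equal to 25.91 months post-enrollment".

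Section 9 plans Month 36 analyses in the end-of-Stage-1 report. Item 4(c) reads "Repeat 1(b)–(c) except for the month 7–36 period and the PP cohort", and items 4(e) and (g) do the same for MITT months 0–36 and FIS months 13–36. The target data cut is 28 May 2021, three days after the last woman's Month 24 target date. The 8.1 methods that 8.2.3 repeats include "additive-difference vaccine efficacy over time, defined as the difference (placebo minus vaccine) in cumulative incidence by time" t.

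**The concern.** Visits are spread over a window. If a woman tests negative early in the window and has no later test, test-date censoring removes her at once. An infection drawn later in the same window is then divided by a risk set that no longer counts her, although she was tested at that visit and found uninfected. The hazard for that visit comes out too high.

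With complete follow-up only dropout produces such women. When the data are cut while women are still between Months 24 and 36, there are many at each of the Month 24, 27, 30 and 33 visits. The same Month 24 data then give a higher hazard in a 7–36 analysis than in the primary analysis.

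At stake are the reported cumulative incidence curves through Month 36 in each arm, and the additive-difference VE, which v1.1 of the SAP added for its attributable-risk and public-health reading. Both are pushed in one direction.

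**Working it through.** **Figures in the SAP that can be reproduced.** The v3.2 rule kept 166 of 969 vaccine and 159 of 1008 placebo recipients: 1 − 166/969 = 82.9% and 1 − 159/1008 = 84.2% lost, matching the stated loss of more than 80%. The Month 24 edge is (728 + 60)/(365/12) = 25.91 months, as stated. The SAP gives no figure for bias in the Month 36 analyses.

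**Closed form for one visit.** Let q be the true probability of infection found at a visit, and r the fraction of women tested there who are tested again later. With tests spread evenly over the window and test-date censoring, the risk set falls linearly from N to rN. The Nelson-Aalen increment is then q × ln(1/r)/(1 − r) instead of q. The multiplier is 1.12 at r = 0.8, 1.19 at r = 0.7 and 1.39 at r = 0.5.

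**Hand calculation, months 7–36, end-of-Stage-1 cut.**

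- From the protocol's sample size section: 10% annual dropout, visits about every 3 months, accrual at half rate for the first 3 months.
- Assumed: 19 months' accrual. Total duration of about 57 months ending around July 2022 implies a start in late 2017. The last Month 24 target of 25 May 2021 implies last enrolment about 28 May 2019.
- Dropout alone gives r = exp(−0.025) = 0.975 and a multiplier of 0.025/0.0247 = 1.0125.
- In months of full-rate accrual, 16 + 1.5 = 17.5 can reach Month 24, 14.5 Month 27, 11.5 Month 30, 8.5 Month 33 and 5.5 Month 36.
- Including dropout, r at Months 24, 27, 30 and 33 is 0.808, 0.774, 0.721 and 0.631. The multipliers are 1.11, 1.13, 1.17 and 1.25. At Month 36 the edge rule gives 1.
- Weighting by days from 196 to 1092 (896 days): [441 × 0.0125 + 91 × (0.1105 + 0.1339 + 0.1726 + 0.2477)]/896 = 66.0/896 = 7.4% on the cumulative hazard, or about 7% on cumulative incidence.
- If every woman can reach Month 36, only the dropout term remains: (896 − 91)/896 × 1.25% = 1.1%.

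**Simulation.** Large-sample runs used the Appendix E test days, 4.2% placebo incidence, VE of 25% to Month 7 and 50% after, 10% dropout and 5% per-protocol loss. Visit scatter was assumed to be −14 to +18 days unless stated. The reference is the same estimator with no dropout or data cut. Ranges cover both arms and the windows 0–36, 7–36 and 13–36 (to tau in Case 2).

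| Scenario | Arm incidence | Additive difference |
|---|---|---|
| 14-month accrual, Stage 1 cut (67 and 71 per arm at Month 36: Case 2, tau 32.9 months) | +8.2 to +14.3% | +9.8 to +13.9% |
| 19-month accrual, Stage 1 cut (256 and 271 per arm: Case 1) | +5.5 to +8.8% | +6.9 to +9.1% |
| Same, scatter ±3 days | +4.5 to +7.0% | +5.4 to +7.1% |
| Same, no scatter | 0% | 0% |
| 19-month accrual, cut 3 months later | +4.1 to +6.2% | +4.5 to +5.9% |
| 19-month accrual, cut 6 months later | +2.8 to +4.0% | +2.9 to +3.7% |
| All women can reach Month 36 | +0.9 to +1.4% | +0.8 to +1.6% |

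With 10% missed visits the last row rises to about 2%. The 14-month accrual gives larger values at the later cuts too: about 8% for months 7–36 three months on, and somewhat more for 13–36.

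For months 7–36 in the 19-month Stage 1 row, the additive difference is 0.0510 against 0.0474. Ratio VE is 0.484 against 0.482, and it moved by less than 0.01 in every run. With every last negative test carried to its window edge, the bias was within about 0.4% where that was run.

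**The case against.** **Timing.** The SAP places the final efficacy analysis after the last woman reaches Month 36, and the Month 36 secondary objectives apply only if Stage 2 occurs. The bias there is about 1–2%. Cases 1 and 2 were also written in May 2022, after a final analysis for which v3.3 says all women had follow-up well beyond Month 24. This stands, and it rules out a single headline percentage. A reader might infer that every Month 36 estimate is about a tenth too high; the documents do not support that. Truncated follow-up is nevertheless planned in Section 9. It also follows under protocol 6.3.1 if Stage 2 does not occur, and Case 2 provides for it: with full follow-up the design yields over 800 per arm at Month 36, far above 150.

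**The 150-per-arm rule.** A reader might infer that Case 2 revives a construction v3.3 rejected. It does not. v3.3 calls the rule appropriate for partial follow-up and drops it only for the final Month 24 analysis. Case 2 also censors women tested at or after tau at tau itself. What remains is that tau can fall inside a visit window.

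**Outputs.** Section 9 items 4(c), (e) and (g) list cumulative incidence and cumulative VE, with no additive-difference output and no test. The MITT 0–36 analysis repeats 8.2.1, which has no additive measure. The additive bias therefore arises only where 8.2.3 repeats the 8.1 methods.

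**Ratio VE.** It is essentially unchanged, because the inflation is nearly equal in the two arms. The runs held VE constant after Month 7; a changing VE would give late intervals too much weight.

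**Conclusion.** The point holds, conditional on the data cut. Test-date censoring before the terminal visit biases arm-level cumulative incidence through Month 36 upward, and the additive-difference VE with it where that is computed. The size is about 5–15% at the end-of-Stage-1 cut, about 2.5–8% with 3–6 more months, about 1–2% when all women can reach Month 36, and zero if visits fall exactly on their target days.

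The direction follows from the rules as written. The size rests on assumed accrual span, visit scatter and data cut, since the visit windows are in the Study Specific Procedures and the final cut date is not stated. The primary Month 24 analysis is essentially unaffected: it uses the edge rule at its own terminal visit, and only dropout acts before that. No hypothesis test or stage decision changes. This is a correction to supplementary and secondary descriptive estimates, worth making because it is cheap and the error runs one way.

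**What to change.** For the Month 36 cumulative incidence and VE analyses in SAP 8.2.3 and in Section 9 items 4(c), (e) and (g):

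- Carry each woman's last HIV-negative test to the right edge of that scheduled visit's window. An equivalent is to time events and censorings by scheduled visit, with events first at ties.
- In Case 2, keep the 150-per-arm criterion but set tau at the right edge of the last scheduled visit that meets it.
- Leave person-year rates on time to the last negative test, including the Month 30 items 4(b), (d) and (f), which repeat only the incidence rate in 1(a).
- If the edge rule is used, tabulate the edge for every visit. The SAP now implies 60 days after target at Month 24 in 8.1, 28 days for the last participant in Section 9 (25 May to 22 June 2021), and about 18 days at Month 36 (36.5 × 365/12 = day 1110 against target day 1092). These should be reconciled or explained.

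The cost is a few sentences and one derived time variable, with no new data. Reported cumulative incidence will be slightly lower.
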